Furthermore, in the UK START study, post mastectomy patients were included as well as patients requiring regional nodal irradiation although only 15% of the enrolled patients were post-mastectomy patients and only 15% of the entire cohort needed regional nodal irradiation. Therefore, these patients at relatively higher risk for lymphedema/brachial plexopathy from XRT were under-represented in the UK START study. However, among the small number of patients treated with hypofractionated XRT to the regional lymph nodes (supraclavicular radiaton), there were no significant increases in lymphedema or brachial plexopathy compared to women treated with standard 5 weeks of XRT to the supraclavicular fossa.[6]

Additionally, a now standard boost dose to the lumpectomy cavity or chest wall, proven to significantly improve local control by 10% or greater in women less than 50 years of age [14-16], was not required in either arm of the Canadian or UK study. [4, 5] The boost dose has been shown to improve locoregional control in all patients by a minimum of 3% but appears to have the greatest impact in younger patients.[14-16] This boost dose has extended conventional XRT treatment from 5 (50 Gy in 25 fxns) to 6 weeks (60 Gy in 30 fxns) in the majority of patients treated within the United States.

At our institution, we have one of the largest experiences with simultaneous integrated boost (SIB) technique in patients with BrCA; we deliver 45 Gy in 25 fxns to the whole breast while treating the cavity simultaneously to a higher dose of 59.92 Gy in 25 fxns. Our published experience shows that at 3 years, our 5-week regimen is generally well tolerated with <1% of patients developing Grade 3 cutaneous toxicity and only 2.8% of patients recurring locally.[17] Our results are particularly important given that 39% of these patients were AA, 33% were premenopausal, 30% had breast separation >25cm, and 45% received chemotherapy, all factors associated with heightened skin toxicity from XRT. [17]

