Seeking to shorten the treatment course further and improve convenience and treatment adherence, we propose to build upon our experience and the level I evidence advocating for hypofractionation in 15 days of treatment. Our proposed study will utilize the SIB technique with the whole breast treated to 40 Gy in 15 fractions and the cavity boosted simultaneously to 48 Gy in 15 fractions. Only one previous study has examined the feasibility of a similar fractionation with the whole breast treated to 40.5 Gy in 15 fractions, while the cavity is treated to 48 Gy.(20) At 1 year median follow-up time, 67% of patients had developed reversible grade 1-2 skin dermatitis and only 1 of 91 patients had recurred locoregionally.(20) However, only 1/3 of patients received chemotherapy and less than a quarter had large breast size. The majority of patients were over the age of 50 and 87% were Caucasian.(20) No study has examined the feasibility of a 15-day hypofractionated SIB XRT regimen in women at high risk for cutaneous toxicity (e.g. women below the age of 50, African American, and/or treated with chemotherapy). The unique patient population served by Emory will enable a study of SIB XRT given 12/13/2016

over 15 treatments. Quality of life measures (e.g. Multidimensional Fatigue inventory (MFI)[18], the Pittsburgh Sleep Quality Index (PSQI) [19], the perceived stress scale (PSS)[20], the Inventory of Depressive Symptomalogy-Self Reported (IDS-SR)[21], the Short-Form Health Survey (SF-36)(25) and the Godin Leisure Time Questionnaire (GLTEQ)(26)) which have been validated in multiple populations, will also be assessed in these patients to determine if 15 days of treatment is feasible.

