# Study Design:

Eighty breast cancer patients with Stage 0-III BrCA treated with breast conserving surgery or mastectomy and clear margins will be recruited to the study. Patients must have **one or more** of the following characteristics and be eligible for breast or chest wall with or without regional nodal radiotherapy:

1. Prior Chemotherapy for Breast Cancer

2. >25 cm of breast separation (the largest distance on an axial slice of the planning CT simulation scan between the entry and exit points of the radiation beam on the body)

- 3. Non-Caucasian Race
- 4. 4.
- 5. Requiring regional nodal irradiation without evidence of N3 disease

Because the above characteristics in isolation have been correlated with heightened levels of skin toxicity and/or were under-represented in previous trials of hypofractionated XRT, any patient fulfilling one of the above criteria, will be approached for enrollment in the study.

Males will be excluded.

To protect against possible side effects of radiation, women who are pregnant or nursing a child may not take part in this study.

Patients who have not received chemotherapy may start XRT up to 16 weeks after lumpectomy surgery. Patients who receive adjuvant chemotherapy after lumpectomy may start XRT up to 7 weeks after their last cycle of chemotherapy.

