**Data**

The SIB dataset was queried, and after exclusion and inclusion listed in the selection diagram file. Total 75 cases were included.

Selection and Exclusion Criteria	Sample Size	Excluded
SIB radiotherapy for breast cancer cases	75	-

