**Outcome and definition**

1. Skin Thickening Ratio (STRA) Baseline
2. Skin Thickening Ratio (STRA) at 1 year
3. Change in Skin Thickening Ratio (STRA) from Baseline to 1 year
4. Overall Survival was defined as months from the date of radiation ended to death or last seen at Emory.
5. Local Recurrence-free Survival (LRFS) was defined as months from the date of radiation ended to local recurrence or last seen at Emory.
6. Distant Recurrence-free Survival (DRFS) was defined as months from the date of radiation ended to distant recurrence or last seen at Emory.

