### **Statistical Analysis**

Statistical analysis was conducted using SAS Version 9.4, and SAS macros developed by Biostatistics and Bioinformatics Shared Resource at Winship Cancer Institute. Descriptive statistics for each variable were reported. Association between variables of interest and the study cohort were examined using ANOVA for categorical variables and Pearson correlation coefficient for continuous variables. Multi-linear regression between variables of interest and the study outcomes was examined. Variables were selected based on statistical significance on univariate analysis, while accounting for multicollinearity and removing variables with high rates of missing data.

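### The SAP's multi-linear regression on the study outcomes does not exclude the censored survival times, and local recurrences are likely too few to support covariate selection by any method

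*SAP*

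**What the plan says.** The SAP's Outcome and definition section lists six outcomes. Three are STRA measures (baseline, 1 year and change). The other three are OS, LRFS and DRFS, each measured in months from the end of radiation. For the local endpoint: "Local Recurrence-free Survival (LRFS) was defined as months from the date of radiation ended to local recurrence or last seen at Emory". For the distant endpoint: "Distant Recurrence-free Survival (DRFS) was defined as months from the date of radiation ended to distant recurrence or last seen at Emory". Neither definition sets a time horizon.

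The Statistical Analysis section says that "Multi-linear regression between variables of interest and the study outcomes was examined" and that "Variables were selected based on statistical significance on univariate analysis". Besides descriptive statistics, it names ANOVA and Pearson correlation. It does not say which outcomes enter the regression, excludes none, and mentions no Kaplan-Meier, log-rank or Cox method. It gives no significance threshold, number of candidate covariates or minimum number of events. The Data section gives the sample: "Total 75 cases were included".

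The protocol's Background cites two earlier series. The institution's 5-week integrated-boost series had "only 2.8% of patients recurring locally", reported at 3 years. In an earlier 15-fraction integrated-boost study, "only 1 of 91 patients had recurred locoregionally" at 1 year median follow-up. Local control is a secondary outcome of the protocol.

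**The concern.** Two faults arise if the regression sentence is applied to every listed outcome.

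The first is censoring. In a linear model of months, a patient last seen free of recurrence at 20 months is treated as if 20 months were her outcome. Most of what is modelled is then length of follow-up. This is wrong for OS, LRFS and DRFS whatever the event count.

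The second is information. Replacing the linear model with a Cox model cures the censoring fault but not a shortage of events, and for LRFS the protocol's own background figures point to a shortage. Selection on univariate significance makes this worse, because with very few events significance depends on where one or two patients happen to fall.

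The trial population was chosen because earlier hypofractionation trials under-represented it. A spurious predictor of local recurrence could be read as showing which of these women do poorly on the 15-fraction regimen.

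**Working it through.** Neither document states an expected event count or power for LRFS, so there is no planned figure to reproduce.

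**Inputs.** n = 75 (SAP, Data). Local recurrence 2.8% at 3 years and locoregional recurrence 1/91 = 1.1% at 1 year median follow-up (protocol, Background). Assumptions: constant hazard; all 75 followed to each horizon (earlier censoring would lower the counts); the 1/91 figure read as a 1-year risk; two-sided 0.05; a covariate split 50:50 for power.

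**Expected events = n × rate.**
- 75 × 0.028 = 2.1 at 3 years. Binomial(75, 0.028): P(none) = 12%, P(4 or fewer) = 94%, central 95% range 0 to 5.
- 75 × 1/91 = 0.8 at 1 year; central 95% range 0 to 3.
- If 2 of 75 recur, the estimate is 2.7%, exact 95% CI 0.3% to 9.3%.

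**Longer follow-up.** Events at t years = 75 × (1 − exp(−ht)), with h = −ln(1 − 0.028)/3 or h = −ln(1 − 1/91). The last column doubles the first hazard as an assumed allowance for a higher-risk mix.

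| Years | 2.8% at 3 years | 1/91 at 1 year | 2.8% hazard doubled |
|---|---|---|---|
| 1 | 0.7 | 0.8 | 1.4 |
| 3 | 2.1 | 2.4 | 4.1 |
| 5 | 3.5 | 4.0 | 6.8 |
| 10 | 6.8 | 7.8 | 12.9 |

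**Censoring.** With 2 events, 73 of 75 LRFS values (97%) are times last seen. With 8 events, 67 of 75 (89%) still are.

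**Power of a Cox model for one covariate.** Schoenfeld: power = Φ(√(d/4) × ln HR − 1.96), where d is the number of events.

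| Events | HR 2 | HR 3 | HR 5 |
|---|---|---|---|
| 2 | 7% | 12% | 21% |
| 7 | 15% | 31% | 57% |
| 10 | 19% | 41% | 72% |

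For 80% power, d = 4 × (1.96 + 0.84)² / (ln HR)², which gives 66 events for HR 2 and 27 for HR 3. With 2 events the HR would have to be about 53.

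**Screening.** With 2 events and a covariate present in 37 of 75, the smallest attainable Fisher p is (37 × 36)/(75 × 74) = 0.24, so a balanced covariate can never be selected at 0.05. With a covariate present in 15 of 75 it is (15 × 14)/(75 × 74) = 0.038, so an uncommon characteristic is selected if both events fall in it. Ten independent null candidates tested at 0.05 give a nominal 1 − 0.95¹⁰ = 40% chance of at least one false positive. The number of candidates is an assumption, since the SAP gives none.

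**The case against.** The strongest reply is that the SAP never says LRFS was regressed. ANOVA, Pearson correlation and linear regression suit the continuous STRA outcomes, which are listed first, and the survival analyses may simply be undescribed. That reading is fair. A reader might infer that predictor models were run on the recurrence endpoints, and the documents do not establish this. What stands is that the sentence covers the study outcomes without exception, and beyond descriptive statistics the survival outcomes have no other stated analysis. The text needs correcting on either reading.

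The second reply is that two events is not this trial's forecast. The 2.8% comes from a different, 5-week regimen. The 1/91 is locoregional, from a cohort that was mostly over 50, with one third given chemotherapy. The present trial planned for "Eighty breast cancer patients with Stage 0-III BrCA treated with breast conserving surgery or mastectomy" and includes patients needing nodal irradiation. LRFS has no horizon, and optional assessment may run to 10 years. This stands, so the count is a range and depends on follow-up. It does not rescue the model: the background rates give at most 7.8 expected events at 10 years, and even the doubled hazard at 10 years (12.9) is under half the 27 events needed for 80% power on a single HR of 3.

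The third reply concerns importance. Local control is secondary, no stated objective concerns its predictors, and the primary safety conclusion does not depend on such a model. This also stands and limits the weight of the point.

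**Conclusion.** The point holds in a limited form. As written, the regression sentence takes in censored times and ignores censoring; this applies to OS, LRFS and DRFS and needs no assumption about event numbers. For LRFS, about 2 local events are expected at 3 years and roughly 1 to 8 over 1 to 10 years, given the background rates and a constant hazard. That cannot support univariate screening or a multivariable model, whether linear or Cox.

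Two stronger conclusions are not supported. A reader might extend the event-count argument to DRFS and OS, but neither document gives an expected distant-recurrence or death rate for this trial, and with stage III included those counts could be higher. A reader might also conclude that any predictor found would be pure noise, or that estimates would be infinite. The calculation shows only that a selected predictor would be unreliable. Infinite estimates are a risk of Cox or logistic models with sparse events, not of the linear model that the SAP names.

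**What to change.** In the SAP's Statistical Analysis section:

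- Name the outcomes that enter the multi-linear regression, and restrict it to the continuous STRA outcomes.
- Report LRFS, DRFS and OS as event counts and as Kaplan-Meier (or cumulative incidence) estimates with 95% CI at a stated time. If the 2.8% figure is shown alongside, say that it comes from another regimen and cohort.
- Do no covariate selection for LRFS.
- If DRFS or OS is modelled, use a method for censored data, limit the covariates to what the observed event count supports, and label the result exploratory.

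The SAP is written in the past tense, so any such models already fitted should be reported as exploratory with their event counts shown.

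The cost is a few sentences of SAP text. Exploratory predictor models for local recurrence are given up; on these numbers their results could not be relied on.

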Information regarding disease characteristics (including stage, tumor size, grade), patient demographics (including age, race, co-morbidities, social history, body mass index), systemic treatment (including hormone therapy, systemic therapy), surgical treatment, radiation treatment, and clinical outcomes (local control, distant metastasis, survival, and treatment complications) will be collected and recorded.

Patients may also be asked to participate in a long term assessment between 1 and 10 years where they will complete the same study procedures as outlined above. Patients will be compensated \$50.00 for completing this visit.

A follow up phone survey will be taken between 18 months and 10 years after treatment. Using the same scales as in the study visits, the patients will be asked to rate their fatigue level, breast pain, how happy they are with the look of their breast and how different their radiated breast is from their non-radiated breast. They will also be asked if they are on any hormonal treatment for breast cancer and if so, the date they started. We will obtain verbal consent for this survey from patients who completed this study before the follow up phone survey was originally approved on 9/24/2013.

Assuming 10% of patients dropout, 53 patients requiring breast only radiation will be enrolled (2-3 patients per month) to yield a total of 50 patients.

An additional 33 patients requiring regional nodal irradiation and breast or chest wall radiation will be enrolled. Assuming 10% of patients dropout, 33 patients of these patients will be enrolled (2-3 patients per month) to yield a total of 30 patients receiving regional nodal irradiation and breast or chest wall radiation.

In patients undergoing regional nodal irradiation, arm measurements will be taken of the ipsilateral and contralateral upper extremity at baseline, 7 - 12 weeks, and 12 – 18 months post XRT by a licensed lymphedema therapist or study staff trained by a licensed lymphedema therapist. These patients will also be assessed for brachial plexopathy using RTOG grading toxicity, LENT/SOMA grading toxicity, and a modified version of a validated questionnaire to assess symptoms of brachial plexopathy at baseline and 7 - 12 weeks, and 12 – 18 months post XRT.[24] If a patient develops RTOG or LENT/SOMA Grade 3 toxicity, an objective measurement (MRI and/or nerve conduction studies) of brachial plexopathy will be employed.

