There is no drug in the proposed study. Our department has 7 linear accelerators all capable of delivering hypofractionated external beam radiotherapy. We also have extensive experience treating patients with simultaneous integrated boost radiotherapy. As determined by 2000 census, the majority of minorities in our community are African American, and African Americans make up 61.4% of the population of metropolitan Atlanta. A study including this population would be feasible. At the three Emory radiation centers, there are approximately 350 patients seen annually with 200 patients having early stage breast cancer. With approximately 80 African American breast cancer with Stage 0-II patients treated annually at Emory Clifton Campus, Emory Midtown, and Grady Memorial Hospital. In a recent study, over 60% of our patients had breast separation >25cm. [17] This trial should be able to accrue 33 high risk patients (2 to 3 patients per month, and assuming a 10% dropout rate) needed to assess the feasibility of this novel hypofractionated simultaneous integrated boost (SIB) regimen.

[name] (co-PI) is an NIH funded physicist with expertise in ultrasound tissue characterization (UTC) of radiation induced cutaneous toxicity. [name] Imaging Laboratory is fully equipped with three clinical ultrasound machines including a state-of-the art Sonix RP scanner with raw radiofrequency echo signals and advanced research interface. The laboratory is located on the tunnel level within the Department of Radiation Oncology. It comprises 500 sq. ft. and is equipped with ultrasound data acquisition system and calibration targets. UTC measurements will be easily performed in patients using [name] equipment and software. Measurements of breast tissue take about 10 minutes to complete.

The MFI, PSS, PSQI, IDS-SR, SF-36 and GLTEQ, and LENT SOMA are surveys which have been validated in various populations and take 15 minutes to complete in total.

Blood for inflammatory markers is routinely processed within the laboratory of my research mentor, [name], Professor of Psychiatry and an international expert on inflammatory induced behavioral changes. He has agreed to help process the blood from this study.

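### Because entry requires at least one listed criterion, the SAP's univariate screen can understate the effects of race, chemotherapy and breast separation on skin thickening and may wrongly drop them

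*SAP*

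**What the plan says.** Protocol, Study Design, requires one or more listed characteristics: prior chemotherapy, breast separation above 25 cm, non-Caucasian race, an item 4 that is blank in the text available to me, and "Requiring regional nodal irradiation without evidence of N3 disease". One is enough: "any patient fulfilling one of the above criteria, will be approached for enrollment in the study". The stated reason is that the characteristics "have been correlated with heightened levels of skin toxicity and/or were under-represented in previous trials of hypofractionated XRT". The list therefore mixes skin-toxicity factors with factors chosen for representation.

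SAP, Outcome and definition, lists STRA at baseline, at 1 year, and the change between them. SAP, Statistical Analysis, tests associations one variable at a time and then fits multiple linear regression: "Variables were selected based on statistical significance on univariate analysis", with allowance for multicollinearity and removal of variables with much missing data. It names no candidate variables and no significance threshold. It does not force in any entry criterion or mention the dependence that the entry rule creates. SAP, Data, gives 75 cases.

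**The concern.** A Caucasian participant is in the trial only because she had chemotherapy, a large separation, nodal irradiation or another listed criterion. Comparing her STRA with that of a non-Caucasian participant is therefore not a comparison of factor absent with factor present. The reference group is enriched for the other criteria. Where those also thicken skin, the unadjusted race contrast shrinks, and the same holds for chemotherapy and separation. A univariate screen decides on exactly this contrast.

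Protocol, Background, argues that race, chemotherapy and breast size raise cutaneous toxicity. A report that one of them showed no association with skin thickening could reflect the entry rule combined with the screen. If a factor is screened out, the coefficients of those that remain are no longer protected either. The primary toxicity rates are not affected.

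**Working it through.** The documents give no effect size, threshold or power for these regressions, so there is no planned figure to reproduce. The check asks how far the entry rule moves a univariate coefficient from a true value of 1.

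**Inputs**
- Source prevalences, from the institutional series in Protocol, Background: "39% of these patients were AA, 33% were premenopausal, 30% had breast separation >25cm, and 45% received chemotherapy". I use race 0.39 (the African American share as a proxy for non-Caucasian), chemotherapy 0.45 and separation 0.30. A possible fifth factor is set at 0.33, an assumption.
- Separation, alternative value 0.60. The protocol's feasibility text, citing the same reference, says "over 60% of our patients had breast separation >25cm".
- Nodal irradiation, low value 0.15, borrowed from the UK trial: "only 15% of the entire cohort needed regional nodal irradiation". High value 30/80 = 0.375, from Protocol, Data Collection: "to yield a total of 30 patients receiving regional nodal irradiation and breast or chest wall radiation". I give it no skin effect.
- Assumed: independent factors and equal additive effects.

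**Formula.** For factor j, let T be the summed prevalence of the other factors that affect skin, and E = 1 − ∏(1 − p) over all the other criteria. Participants with factor j carry T other skin factors on average. Those without it carry T/E, because they needed another criterion to enter. The univariate coefficient is 1 + T − T/E.

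**Three factors**
- Race: T = 0.45 + 0.30 = 0.75; E = 1 − 0.55×0.70 = 0.615; T/E = 1.22; coefficient 0.53. Chemotherapy prevalence is 45% in non-Caucasian participants and 0.45/0.615 = 73% in Caucasian participants.
- Chemotherapy: T = 0.69; E = 1 − 0.70×0.61 = 0.573; coefficient 0.49.
- Separation: T = 0.84; E = 1 − 0.55×0.61 = 0.6645; coefficient 0.58.

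**A neutral criterion.** Participants with nodal irradiation carry 0.45 + 0.30 + 0.39 = 1.14 skin factors. Those without carry 1.14/(1 − 0.55×0.70×0.61) = 1.49. The contrast is −0.35 although the true effect is zero.

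**All scenarios**

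| Scenario | Chemotherapy | Separation | Race | Nodal (true 0) |
|---|---|---|---|---|
| Three factors, separation 30% | 0.49 | 0.58 | 0.53 | n/a |
| Three factors, separation 60% | 0.68 | 0.58 | 0.70 | n/a |
| Plus nodal 15% | 0.61 | 0.66 | 0.64 | −0.35 |
| Plus nodal 37.5% | 0.75 | 0.78 | 0.76 | −0.35 |
| Five factors, nodal 15% | 0.67 | 0.72 | 0.70 | −0.27 |
| Five factors, separation 60%, nodal 37.5% | 0.85 | 0.81 | 0.86 | −0.17 |

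The rows with nodal irradiation use separation at 30% unless stated. In the last row the assumed fifth factor has coefficient 0.87, the top of the 0.49-0.87 range.

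**Screening loss for race.** Simulated with n=75, 0.6 SD per factor, two-sided p<0.05 and independent factors:
- three factors: dropped in 76%, mean univariate estimate 0.32 SD
- plus nodal irradiation at 37.5%: about 55-57%, 0.45 SD
- five factors, nodal 15%: 62%, 0.42 SD
- five factors, separation 60%, nodal 37.5%: about 48-51%, 0.51 SD
- same scenarios without the entry rule: 34-40%

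With all three factors forced into the three-factor case, the race estimate is 0.60 SD and power is 64%.

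**Source correlation.** At a latent correlation of 0.3, coefficients for the skin factors are 0.66-0.88 with three or four factors and 0.92-1.06 with five. At 0.5 with five factors they are 1.12-1.31.

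**The case against.** A reader might infer that the screen is bound to understate and discard the risk factors. The documents do not support that, for four reasons.

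First, the direction is not fixed. The documents give no correlations between the criteria. If they cluster in the source population, the understatement shrinks, vanishes or turns into overstatement, as the correlation results show. This stands. It does not rescue the screen, because the unadjusted contrast is then wrong in the other direction.

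Second, the other criterion need not be a skin-toxicity factor. Nodal irradiation qualifies alone, and the protocol's rationale includes under-representation. This stands and weakens the attenuation: with nodal irradiation at 37.5% the race coefficient is 0.76 rather than 0.53.

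Third, much of the loss is ordinary small-sample screening. Race fails in 34-40% of simulations without the entry rule, and in the fullest five-factor scenario the rule moves that only from about 40% to about 51%. At n=400 race is dropped in 0-15% of simulations, and the retained factors then adjust for each other. So the distortion of the unadjusted contrast does not depend on sample size, but the dropping largely does.

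Fourth, the SAP never says that race, chemotherapy and separation are among its variables of interest, and estimating their effects is not a stated protocol objective. That they pass through the screen is an inference. It is a reasonable one, since they define the population and the protocol collects race and systemic treatment. If they were never candidates, the models omit them altogether and the remedy is the same.

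**Conclusion.** The point holds as a risk, not a certainty. Entry on any one criterion distorts the unadjusted contrasts that decide what enters the STRA models, and the SAP has no safeguard. Under independence and equal additive effects the univariate effect is about 49-87% of the true one. At n=75 and 0.6 SD, race is lost in about 48-76% of simulated trials, against 34-40% without the rule. A neutral criterion can appear protective, by 0.17-0.35 of one factor's effect.

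The low end of the coefficients and the high end of the drop rates belong to the case of only three independent factors and should not be quoted alone. The figures also rest on the proxy for race, an assumed threshold, and STRA being available for all 75 cases. Fewer STRA values would raise the drop rates.

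Under the additive model, a regression holding every entry criterion is free of this bias, because selection then depends only on variables in the model. That is so whatever the source correlation. It does not make n=75 ample: in the three-factor case it still misses a 0.6 SD race effect about 36% of the time.

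**What to change.** In SAP, Statistical Analysis:
- Prespecify all the entry criteria in Protocol, Study Design (prior chemotherapy, separation, race, nodal irradiation, and item 4 as it reads in the full protocol), with separation preferably continuous.
- Force them into every STRA regression, whatever their univariate p-values and without removal at the collinearity step.
- Report their adjusted estimates with confidence intervals.
- Confine any data-driven selection to further variables.
- Label unadjusted comparisons of the entry criteria as descriptive.

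The cost is about 4-5 degrees of freedom out of 75 and a change of SAP wording. The data are already collected. Since the SAP is written in the past tense, any models already fitted would need to be rerun.
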